7.7 SF-12V2 QUESTIONNAIRE MISSING DATA

Rules suggested by the producer of this instrument will be followed in calculating the values. If these rules are not enough to impute a value, and a patient still has a missing value at a visit, the missing values will be assumed to be missing at random.

7.8 FACIT-FATIGUE QUESTIONNAIRE MISSING DATA

If any items are not answered the following approach will be taken:

If more than 50% of the items are non-missing, a prorated subscale will be derived as

$$\text{Prorated Subscale Score} = \frac{\text{Sum of individual answered items} * 13}{\text{Number of answered questions}}$$

If 50% or more of the items are missing the score will be set to missing.

8 STATISTICAL METHODOLOGY AND STATISTICAL ANALYSES

8.1 STATISTICAL METHODS

Visits, defined by [Table 9](#) of Section [11.1](#), will be used for the analyses.

8.1.1 Analysis of Time to Event Data

8.1.1.1 Cox Proportional Hazards

Cox proportional hazards (PH) models will be used to analyse time to event data, where the event of interest is duration of Tofacitinib drug survival described in Section **Error! Reference source not found.** If a patient is not recorded as having permanently discontinued Tofacitinib, which is the event of interest, then they will have their time of follow-up censored at the date of their last visit.

For the primary analysis, univariate Cox PH models will be created for all of the potential predictive factors, see [Figure 2](#) in Section [8.2.3](#), that is a separate Cox PH model will be created for each factor. If the variable significantly impacts Tofacitinib drug survival at the 10% level then the factor will be put forward into a multivariate model.

Once the univariate model selection is complete, backwards selection will be used to remove factors from the multivariate model which do not have a significant p value at the 5% level. The covariate with the highest p value will be removed in turn until all factors have a p value less than 0.05. If a significant interaction is found then the individual factors of this interaction will be kept in the model, regardless of their p value. A significant interaction is tested for between all variables in the multivariate model.

Furthermore, for the primary analysis a table showing all of the 95% confidence intervals and p values for the “raw” hazard ratios coming from the univariate models will be created. This will be for all of the factors in [Figure 2](#), regardless of whether they’re included in the multivariate model.

For the secondary analysis, a multivariate Cox PH model will be created including the scores from the 5 domains of the CSQ at baseline and the total PCS score at baseline included as covariates.

A further two Cox PH models will be produced for the secondary analysis, for CSQ and PCS: the first including the last evaluation available before discontinuation (or last visit if

patient does not discontinue during the study) and the second including change from baseline to the last recorded measurement.

The SAS procedure PROC PHREG will be used to fit any Cox PH models and check the assumption of proportional hazards. If the assumption of proportional hazards is violated then alternative models will be considered.

Hazard ratios (HRs) and the 95% confidence intervals (CIs) will be created and displayed, along with the associated p value from the models. All statistical tests will be two-sided with alpha of 0.05, apart from during variable selection using univariate models for the primary analysis, where alpha will be considered as 0.1. Two-sided CI's will be presented whenever it is appropriate. No adjustment for multiplicity will be used.

Drug survival with Tofacitinib will be described with the Kaplan-Meier (KM) method, using the SAS procedure PROC LIFETEST. Confidence intervals will be displayed, using the Klein and Moeschberger method. An estimate for drug survival at 12 and 24 months will be presented. A KM plot will be created to display the survival function of the Tofacitinib Total group. As a sensitivity comparison a KM plot will also be presented showing the Tofacitinib as Monotherapy group and the Tofacitinib as Combination Therapy group.

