9.5. Sample size

The primary objective of this study is to identify factors predictive of drug survival. This will be investigated using a multivariate Cox regression model. A review of the literature suggests that such an analysis requires at least 10 events (discontinuation of treatment) per variable proposed in a multivariate regression model⁽⁴⁸⁾. The minimum number of subjects to include in the study can then be estimated using the following formula:

$$N = 10 k / p$$

Where p is the smallest of the proportion of positive cases (cases that reached the endpoint) and negative cases (cases that did not reach the endpoint) in the population and k the number of predictor variables.

Assuming a drug survival of 50% at 24 months⁽²⁴⁾ and also that 30% of the potential predictive factors will pass the univariate selection, it will be necessary to observe 150 events (i.e. 50 x 0,3 variables x10 events) in approximately 300 patients (i.e. 150 events/0.50).

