First, the effect of each factor on drug survival will be tested with a univariate Cox model. Thus, the hazard-ratios calculated are called “raw”. They will be presented with their 95% confidence interval and their associated p-value. Then, all potential factors for which the p-value resulting from univariate analysis is strictly less than 10% will be included in a multivariate Cox model. Predictive factors and their interactions will be chosen using a backward (step-down) selection. Predictive factors chosen will be those which have a p-value < 5%. In the case of a significant interaction, all individual components of the interaction will be “forced” in the model, whether they are statistically significant or not. The adjusted hazards-ratios thus obtained will be presented with their 95% confidence interval and their associated p-value.

Missing data will be managed using a method based on missing data indicators^(50, 51). This method is not a method of imputation of missing data. A fixed value will be assigned to missing observations, and a dummy variable (1/0) will be added to the multivariate model in order to indicate if the value of this variable is missing or not. If more than 10% of the patients have missing baseline covariates, a complete case analysis will also be performed as a sensitivity analysis. Additional methods for handling missing data may also be used. Further details will be provided in the statistical analysis plan as appropriate.

Secondary analyses

The impact of behavioural strategies (catastrophisation and coping) on Tofacitinib drug survival will be evaluated in patients suffering from RA. A Cox proportional hazards model will be used with the 5 dimensions in the coping questionnaire and the catastrophisation score collected at the baseline visit included as independent variables.

In a second phase and in a similar manner, a Cox model will be used to estimate the impact of the adaptive strategies under treatment. Therefore, the last evaluation available before discontinuation of treatment (or the last visit if a patient does not permanently discontinue treatment) and the change between this latter evaluation and the baseline value will be taken into account in separate models.

The correlation between behavioural strategies and effectiveness will be studied with Pearson's or Spearman's coefficient according to the nature of variables compared.

Interim analysis

Interim descriptive analyses will be conducted annually.

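### Interaction testing in the primary Cox model is unrestricted, unadjusted and of unstated stage; at the planned size false interactions are likely and, on two of three readings, many more null factors are kept

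*SAP*

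**What the plan says.** The primary objective is to identify factors predictive of tofacitinib drug survival, and the result is the set of factors retained in a Cox model. SAP 8.1.1.1 sets out these steps:

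- **Screen.** Each candidate in Figure 2 is tested alone: "If the variable significantly impacts Tofacitinib drug survival at the 10% level then the factor will be put forward into a multivariate model".
- **Backward selection.** "The covariate with the highest p value will be removed in turn until all factors have a p value less than 0.05".
- **Interactions.** "A significant interaction is tested for between all variables in the multivariate model". If one is significant, its component factors stay in the model whatever their own p-values.

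Protocol 9.7 has the same forcing rule and puts main effects and interactions into one procedure: "Predictive factors and their interactions will be chosen using a backward (step-down) selection". Both documents rule out any multiplicity adjustment.

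Protocol 9.5 sizes the study on the statement that "such an analysis requires at least 10 events (discontinuation of treatment) per variable proposed in a multivariate regression model", and counts "50 x 0,3 variables x10 events". No interaction terms are in that count.

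**The concern.** The rule puts no limit on the search. The number of pairs grows with the square of the number of factors, every pair is tested at 5%, and each significant pair brings in two main effects that need not be significant themselves. A factor that passed the 10% screen by chance can therefore stay through a chance interaction, although backward elimination would have removed it. The number of terms may also far exceed what the events can support under the protocol's own rule.

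The retained list is the main conclusion of the study. False interactions would appear in it as findings, and they would change the meaning of the adjusted hazard ratios of their components, including those of true predictors.

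**Working it through.** **Inputs.** From Protocol 9.5: 50 candidates, 30% passing the screen, 10 events per variable, and "Assuming a drug survival of 50% at 24 months". From SAP 8.1.1.1: 10% to enter, 5% to stay, no multiplicity adjustment.

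**The plan's own figure.** k = 50 × 0.3 = 15; events = 10 × 15 = 150; N = 150 / 0.50 = 300. This reproduces.

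**Counting interactions.**
- Pairs among 15 factors: 15 × 14 / 2 = 105.
- Terms: 15 + 105 = 120. Events per term: 150 / 120 = 1.25, against 10.
- The protocol's formula applied to 120 terms: 10 × 120 = 1,200 events, and 1,200 / 0.50 = 2,400 patients.

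**Nominal error rates** (no true interaction, independent tests at a true 5% level).
- Expected false interactions: 105 × 0.05 = 5.25.
- At least one: 1 − 0.95^105 = 99.5%.
- A given factor is in 14 pairs, so it is forced in with probability 1 − 0.95^14 = 51.2%. Over 15 factors that is 15 × 0.512 = 7.7.
- With 10 factors: 1 − 0.95^9 = 37.0%. With 5 factors: 1 − 0.95^4 = 18.5%.

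**Simulations at 300 patients and about 150 events.** All assume independent factors with one degree of freedom each and no true interaction.

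*Fifteen factors, all null, all having passed the 10% screen* (normal or binary, 150 runs each). Factors kept:
- no interactions: about 8.1 of 15 (54%);
- each pair added singly to the 15-factor model: 12.1 to 12.3 of 15 (about 81%);
- all pairs in one backward elimination: 13.4 to 13.7 of 15 (about 90%), with about 12 to 14 false interactions.

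*Eleven true and four screened null factors* (assumed log HR 0.25 per SD, 150 runs). This mix matches the plan: if every true factor passes, T + 0.10 × (50 − T) = 15 gives T = 11.1, so about 3.9 null factors pass. Null factors kept:
- no interactions: 1.55 of 4 (39%);
- pairs singly: 3.05 of 4 (76%);
- all pairs together: 3.59 of 4 (90%).

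*Fifty candidates put through the actual screen* (half binary, half continuous, 40 to 100 runs per scenario). Share of screened null factors kept, without interactions and then with all pairs in one backward selection:
- 12 true factors (HR 1.28 per SD), about 14 passing: 34% and 97%;
- 10 true factors: 36% and 79%;
- 6 true factors (HR 1.35): 35% and 71%.

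In the 12-factor case 21% of the interactions had p < 0.05 in the starting model, so with so few events per term the tests run well above 5%.

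**Testing only after selection.** Every component has then already met the 5% criterion, so none is forced in. At least one false interaction was still kept in 71–83% of runs.

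**The case against.** The strongest reply is that the texts do not fix the harmful reading. The SAP describes backward removal before it mentions interactions, so the multivariate model it refers to may be the one left after selection. In that case no null factor is added. This stands as far as the SAP goes, but Protocol 9.7 selects factors and interactions together, so one joint backward selection is the closest reading of the protocol. The ambiguity is itself a gap in a primary analysis.

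A reader might infer that almost all of about 15 factors would be kept whether or not they predict drug survival. The documents do not support that as a general statement. Forcing alone, at a true 5% level, takes in about half. Retention near 90% or above needs all pairs in one elimination and close to 15 factors, and 15 is a planning assumption. If all 50 candidates were null, about 5 would pass and each would have an 18.5% chance of being forced in. Part of the false retention also comes from the 10% screen and exists without any interaction.

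Protocol 9.7 further defines chosen factors by p < 5%, treats forced components separately, and reports p-values, so a non-significant forced effect would be visible. Keeping the components of an interaction is ordinary practice. The SAP also tabulates raw hazard ratios for every candidate, runs random survival forests, and states that there are no formal hypotheses. These points help transparency. They do not remove false interactions that themselves reach p < 5%, and the forests are only a sensitivity analysis, so they do not correct the Cox model. Neither document says how a forced component is to be reported.

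**Conclusion.** The concern holds in a form that depends on the reading. At the planned size the interaction search has 1.25 events per term, against the protocol's 10, and the sample size makes no allowance for it. If all pairs are tested, at least one false interaction is almost certain. If only the surviving factors are tested, one is still likely. Screened null factors are kept in about 35–39% of cases without interactions in the mixed scenarios, rising to about 76–81% with pairs tested singly and about 90% with joint backward selection. In absolute terms, in the mix of 11 true and 4 null factors, about 1.5 to 2 more null factors reach the final model (from 1.55 to 3.05 or 3.59 of 4).

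These sizes assume independent factors with one degree of freedom each, no true interactions and about 15 factors passing the screen. The candidate list in Figure 2 was not visible in the text reviewed, and SAP 8.2.3 itself expects collinearity among the SF-12 scores. Correlated or multi-level factors would change the figures, and fewer screened factors would reduce them.

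**What to change.** Amend SAP 8.1.1.1, and align Protocol 9.7 and the protocol summary:

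1. Select main effects first, with no interactions in the model.
2. Replace the search across all variables with a short list of interactions, agreed in advance with the Scientific Committee and added to the selected model. Say what happens when a listed interaction involves a factor that was not selected.
3. Control the overall error. One option is a single joint likelihood-ratio test of the list, with individual interactions examined only if it is significant. Other methods would also serve if named in advance.
4. State that a main effect kept only for hierarchy is not reported as a predictive factor.

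This is a change of wording and needs no new data. The cost is that unforeseen interactions are not searched for, or are labelled exploratory. By the protocol's own rule, 150 events cannot support that search.

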Study Objectives	
Primary objective:
 
- To identify factors predictive of drug survival with Tofacitinib 
Secondary objectives:
 
- To evaluate the impact of behavioural strategies in patients with rheumatoid arthritis on Tofacitinib drug survival.- To study the correlation between behavioural strategies and effectiveness- To evaluate the effectiveness of Tofacitinib

	
 - To evaluate the tolerability of Tofacitinib 																			
EVALUATION END POINTS	
Primary endpoint
 
 • Duration of Tofacitinib survival 
Secondary endpoints
 
 • Change from baseline in catastrophising behaviour adopted by the patient (PCS-Pain Catastrophising scale) ^(34, 35) • Change from baseline in coping adaptive strategy adopted by the patient (CSQ - Coping Strategies Questionnaire) ⁽²⁹⁻³²⁾ • Percentage of patients with low disease activity (LDA) as assessed by DAS28-4 ESR/CRP < 3.2, SDAI ≤11, CDAI ≤10 ⁽³⁶⁾, • Percentage of patients in remission as assessed by DAS28-4 ESR/CRP < 2.6, SDAI ≤3.3, CDAI ≤2.8, ACR-EULAR 2011 Boolean criteria (TJC ≤ 1 + SJC ≤ 1 + CRP ≤ 1 mg/dL + VAS patient ≤ 1) ^(36, 37) • Change from baseline in DAS28-4 ESR/CRP and its components over time • Evaluation of the response to treatment by considering outcome of DAS28 (EULAR criteria) ⁽³⁸⁾ 																			

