Data Analysis	
STATISTICAL ANALYSES
 
The detailed methodology for conduct of the statistical analysis of data collected in the setting of this study will be documented in a Statistical Analysis Plan (SAP).
 
Tofacitinib maintenance will be estimated by considering the date of initiation of treatment with Tofacitinib and the date of permanent discontinuation. The time of follow-up of patients not presenting with an event of interest (permanent discontinuation of treatment) will be censored at the date of the last visit. Drug survival with Tofacitinib will be described using the Kaplan-Meier method in a full analysis set.
 
Principal analysis
 
Factors predictive of drug survival will be investigated using a Cox model. A univariate analysis will first be conducted. All potential factors for which the p-value resulting from the univariate analysis is strictly less than 10% will be included in a multivariate Cox model. Predictive factors and their interactions will be selected according to a backward (step-down) selection method. Predictive factors retained in the model will be those with a p-value < 5%.
 
Key secondary analysis
 
The impact of behavioural strategies (catastrophisation and coping) on Tofacitinib drug survival will be evaluated in patients suffering from RA. A Cox proportional hazards model will be used with the 5 dimensions of the coping questionnaire and the catastrophisation score collected at the baseline visit included as independent variables.

Effectif	300 patients
Regulatory	RIPH de catégorie 3 CNIL : Méthodologie de référence MR003

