8. STUDY OBJECTIVES

Primary objective of the study

- To identify factors predictive of drug survival with Tofacitinib

Secondary objectives

- To evaluate the impact of behavioural strategies in patient with rheumatoid arthritis on Tofacitinib drug survival
- To study the correlation between behavioural strategies and effectiveness
- To evaluate the effectiveness of Tofacitinib
- To evaluate the tolerability of Tofacitinib

[figure not shown]

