2.4 STUDY OBJECTIVES

The primary objective of this study is to identify factors predictive of drug survival with Tofacitinib in RA patients. To assess this the time (in days) which a patient is being treated with Tofacitinib, up to permanent discontinuation, will be modelled using Cox proportional hazard (PH) models and predictive factors will be investigated to assess their impact on the models.

The secondary objectives are:

- *To evaluate the impact of behavioural strategies in patients with rheumatoid arthritis on Tofacitinib drug survival* by including the PCS (total score) and CSQ (5 domain scores) in a Cox PH model
- *To study the correlation* (by considering relevant correlation coefficients) *between behavioural strategies and effectiveness*
- *To evaluate the effectiveness of Tofacitinib*
- *To evaluate the tolerability of Tofacitinib*

Unless specified otherwise, secondary endpoints will be assessed using summaries only.

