4 HYPOTHESES AND DECISION RULES

The primary and secondary analyses will use predictive models, described in Section 8.2.3 and Section 8.2.5.1, to assess Tofacitinib drug survival. All other summaries will analyse data descriptively.

There are no formal statistical hypotheses for this study.

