8.2.6.1 Behavioural Strategies – PCS and CSQ

The impact of behavioural strategies (PCS total score and 5 domains of the CSQ) on Tofacitinib drug survival will be analysed, using three multivariate Cox PH models as described in Section 8.1.1.1 Cox Proportional Hazards.

PCS (individual domain scores and total scores) and CSQ (individual domain scores) will also be summarised as continuous variables as per Section **Error! Reference source not found.** PCS total score will also be summarised as a dichotomous variable (<20 vs ≥ 20) as per Section **Error! Reference source not found.**

Correlations between the behavioural strategies (PCS total score and 5 domains of the CSQ) and each of the endpoints listed below will be investigated as outlined in Section **Error! Reference source not found.**, for the endpoints seen in Figure 3:

- DAS28-4 ESR
- DAS28-4 CRP
- TJC
- SJC
- Duration of morning stiffness
- GIRERD Questionnaire
- EuroQoL EQ-5D-3L
- SF-12v2 Questionnaire
- FACIT-Fatigue Questionnaire
- DAS28 (EULAR Criteria)
- Pain

Figure 3 Timepoints for correlation analyses

Behavioural Strategies Timepoint	Effectiveness Endpoint Timepoint
M0 (Baseline)	M3
M0 (Baseline)	CFB to M3 (M3-M0)
M3	M3
M3	CFB to M3 (M3-M0)
CFB to M3 (M3-M0)	M3
CFB to M3 (M3-M0)	CFB to M3 (M3-M0)
M0 (Baseline)	M6
M0 (Baseline)	CFB to M6 (M6-M0)
M6	M6
M6	CFB to M6 (M6-M0)
CFB to M6 (M6-M0)	M6
CFB to M6 (M6-M0)	CFB to M6 (M6-M0)
M0 (Baseline)	M12
M0 (Baseline)	CFB to M12 (M12-M0)
M12	M12
M12	CFB to M12 (M12-M0)
CFB to M12 (M12-M0)	M12
CFB to M12 (M12-M0)	CFB to M12 (M12-M0)
M0 (Baseline)	M24
M0 (Baseline)	CFB to M24 (M24-M0)
M24	M24
M24	CFB to M24 (M24-M0)
CFB to M24 (M24-M0)	M24
CFB to M24 (M24-M0)	CFB to M24 (M24-M0)

M = Month. CFB = Change from baseline.

Logistic regression will be considered to assess the relationship between behavioural strategies (PCS total score and 5 domains of the CSQ) and each of the binary endpoints listed below as outlined in Section **Error! Reference source not found.**, with a separate model created for each of the timepoints seen in Figure 4:

- LDA
- Patients in remission
- FiRST Questionnaire

Figure 4 Timepoints for logistic regression

Behavioural Strategies Timepoint	Effectiveness Endpoint Timepoint
M0 (Baseline)	M3
M3	M3
CFB to M3 (M3–M0)	M3
M0 (Baseline)	M6
M6	M6
CFB to M6 (M6–M0)	M6
M0 (Baseline)	M12
M12	M12
CFB to M12 (M12–M0)	M12
M0 (Baseline)	M24
M24	M24
CFB to M24 (M24–M0)	M24

M = Month. CFB = Change from baseline.

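### The key secondary Cox model for baseline PCS and CSQ adjusts for no patient or disease factor, and no adjusted version is prespecified beside it

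*SAP*

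**What the plan says.** The first secondary objective in the Protocol 4 Summary is "To evaluate the impact of behavioural strategies in patients with rheumatoid arthritis on Tofacitinib drug survival"; Protocol 8 repeats it almost word for word. SAP 2.4 meets it "by including the PCS (total score) and CSQ (5 domain scores) in a Cox PH model".

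The Protocol 4 Summary names this the key secondary analysis and specifies a Cox model "with the 5 dimensions of the coping questionnaire and the catastrophisation score collected at the baseline visit included as independent variables". Protocol 9.7 and SAP 8.1.1.1 describe the same model, the SAP as "including the scores from the 5 domains of the CSQ at baseline and the total PCS score at baseline included as covariates". SAP 8.2.6.1 states that the impact "on Tofacitinib drug survival will be analysed, using three multivariate Cox PH models"; the three use baseline scores, last scores and change scores. For the first, SAP Table 8 (8.2.9) lists only baseline CSQ and baseline PCS as covariates, with no missing-data method.

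The sensitivity analyses in SAP 8.2.4 concern only the primary predictor model. On interpretation, SAP 4 says "The primary and secondary analyses will use predictive models" and that there are no formal hypotheses.

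**The concern.** In this model, multivariate means only that the six scores are adjusted for one another. A baseline factor that goes with both catastrophising and earlier discontinuation, such as long or refractory disease, would load onto the PCS and CSQ hazard ratios.

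The SAP studies both halves of that problem but does not join them. Sections 8.1.3 and 8.2.6.5 explore which baseline characteristics go with PCS of 20 or more. Section 8.2.3 tests which baseline factors predict drug survival. A factor that does both would still not enter this model.

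The protocol recognises the issue elsewhere. Its background (Protocol 7) relies on a Swiss registry analysis of drug retention that adjusted for eight patient, disease and treatment-history factors. Protocol 9.9, on limitations, discusses selection bias but not confounding.

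Protocol 7 also says that no data exist on behavioural strategies and DMARD survival. The hazard ratio may therefore be quoted on its own under a heading of impact, with a confidence interval and p-value but no statement that it is unadjusted for patient and disease factors. The risk is a misread secondary result, not a failed test.

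**Working it through.** **1. The plan's own figure.** Protocol 9.5 uses N = 10k/p with k = 50 × 0.3 = 15 and p = 0.50. Events = 10 × 15 = 150 and patients = 150/0.50 = 300. Both reproduce.

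**2. Room for covariates at 150 events.**
- Planned model: 6 terms, 150/6 = 25 events per term.
- Limit at 10 events per term: 150/10 = 15 terms, so 9 can be added.
- Six scores plus age, sex, disease duration, number of previous biologics/tsDMARDs and concomitant csDMARD: 11 terms, 150/11 = 13.6. This falls below 10 once more than (150 − 110)/150 = 26.7% of events are lost.
- Adding DAS28-4 CRP, pain and depression: 14 terms, 150/14 = 10.7. This falls below 10 once more than (150 − 140)/150 = 6.7% are lost.

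**3. Size of the bias.** The documents give no correlations or confounder effects, so every input here is an assumption. One confounder correlates ρ with both PCS and CSQ-Catastrophising, which correlate r with each other. It has log hazard ratio β per SD, and neither score has a true effect. The approximate spurious PCS hazard ratio in the six-score model is exp(βρ/(1 + r)):
- low end: exp(0.199 × 0.3/1.8) = 1.034
- high end: exp(0.399 × 0.5/1.6) = 1.133

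A Cox simulation (300 patients, 150 events, 2,000 runs per row, the other four CSQ domains independent) gives, for the planned model:

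| ρ | Confounder HR | r | PCS HR | Falsely significant |
|---|---|---|---|---|
| 0 | – | – | 0.999–1.002 | 5.0–5.6% |
| 0.3 | 1.22 | 0.6 | 1.046 | 6.8% |
| 0.3 | 1.22 | 0.8 | 1.034 | 6.0% |
| 0.3 | 1.49 | 0.6 | 1.079 | 11.2% |
| 0.3 | 1.49 | 0.8 | 1.062 | 7.2% |
| 0.5 | 1.22 | 0.6 | 1.068 | 10.3% |
| 0.5 | 1.22 | 0.8 | 1.064 | 7.8% |
| 0.5 | 1.49 | 0.6 | 1.130 | 22.2% |
| 0.5 | 1.49 | 0.8 | 1.116 | 13.6% |

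The Monte Carlo standard error near 5% is about √(0.055 × 0.945/2000) = 0.5 points, so 6.0% is not distinguishable from the 5.0–5.6% seen without confounding. Weaker correlations of 0.1 to 0.2 gave a PCS hazard ratio of 1.02–1.05 and false significance of 5.5–8.9%.

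**4. What adjustment would do.** With 11 terms:
- confounder fully captured: PCS hazard ratio 0.996–1.007, false significance 4.8–6.5%
- confounder half captured: 1.019–1.078, 5.2–11.3%

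With the confounder captured, the standard error of the PCS log hazard ratio rises from 0.104 to 0.106–0.110 at r = 0.6, and from 0.138–0.139 to 0.141–0.143 at r = 0.8. That is about 2–6%.

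**The case against.** **The models are predictive.** SAP 4 says so and states no hypotheses, and for a predictive association a model of scores alone is legitimate. This stands: a reader might infer from the word impact that the plan makes a causal claim, and the documents do not support that. What remains is that hazard ratios and p-values will be reported without saying what they are not adjusted for.

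**The primary model may already adjust.** A reader might conclude that these hazard ratios cannot be separated from baseline factors anywhere in the study. The text does not support that either. Figure 2 is not shown. If it contains PCS or CSQ, the primary model would give adjusted hazard ratios, but only for scores that pass the 10% screen and the 5% backward selection. The random survival forest would give variable importance and no hazard ratio.

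**The size is assumed, and the covariates may miss it.** This stands. Nothing in the documents shows that age, sex, disease duration, prior treatment or csDMARD use correlates 0.3 to 0.5 with PCS. Pain, disease activity and depression may be stronger correlates, but Protocol 7 says behaviour can influence symptom intensity, so these may be mediators. It would be wrong to read the 22% as the error that the five covariates would remove. Larger figures also arise if PCS is fitted without CSQ-Catastrophising (hazard ratio up to exp(0.399 × 0.5) = 1.22), but that is not the planned model.

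**Extra analyses are already allowed.** Protocol 9.7 permits them in agreement with the Scientific Committee. That does not prespecify this one, and covariates chosen after the results are seen carry less weight.

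**The registry precedent compared drugs,** which is a different question. It shows which factors the protocol's own source treated as confounders of retention, and no more.

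**Conclusion.** The gap is real and modest. All descriptions of the baseline model agree on six scores and nothing else, and no adjusted version is planned. The hazard ratios may partly reflect baseline differences.

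Under the assumed inputs, the spurious PCS hazard ratio is about 1.03 to 1.13 per SD. The effect on false significance ranges from undetectable to about 22%. With weaker confounding it is smaller still, and the documents cannot say which case applies. An adjusted model should be added because it is cheap and informative, not because the planned result is shown to be wrong.

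**What to change.** Keep the six-score model as the key secondary analysis. In SAP 8.1.1.1, 8.2.6.1 and Table 8:

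1. Add one adjusted Cox model for the baseline scores, with a fixed list taken from SAP 8.2.6.5 and not chosen by p-value: age, sex, disease duration, number of previous biologics/tsDMARDs and concomitant csDMARD.
2. Refit the six-score model on the same complete-case patients, and report patients and events for each fit. Without this, a change in hazard ratio could come from a change in patients. Even then, hazard ratios are non-collapsible, so a shift is not purely confounding.
3. Optionally, add a single sensitivity model with baseline DAS28-4 CRP, pain and depression, labelled as possible mediators, only if at least 10 events per term remain.
4. State that all these hazard ratios, adjusted or not, are associations and not causal impact.

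The cost is SAP wording and a few model runs, with no new data. Some patients will be lost to missing covariates because the secondary analyses use no missing-data method (SAP 8.2.6, Table 8), and PCS and CSQ are themselves not imputed (SAP 7.4, 7.5). If 20% of events were lost (assumed), 120 events would give 120/11 = 10.9 per term for the adjusted model but 120/14 = 8.6 for the optional one, which would then be dropped.
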